As many as 90% of all US managed care organizations (MCOs) report using cost in determining coverage of treatments, drugs, and other interventions, while 40% specifically report the use of cost-effectiveness analyses.⁽¹²⁾ An increasing awareness of the fiscal challenges confronting the Medicare program and other public payors in the US suggest that interventions which improve outcomes and decrease costs will be well-received.⁽¹³⁾ Approval by both public and private payors is therefore a first step in wide dissemination of a new intervention in the US health system. The approval process begins with quantifying an intervention's cost as well as the intervention's cost-efficacy compared to other interventions. Thus, understanding the costs of STELLA will advance the program toward a pragmatic trial and ultimately toward widespread adoption in the US health system.

3. Project Description

Care Partners will participate in an 8-week intervention in which a Guide (e.g., nurse or social worker) will help them identify and modify distressing behavioral symptoms of dementia. We will measure Care Partner affective symptoms, including depression and burden, as well as quality of life for both the Care Partner and the person with dementia. Assessments will occur prior to, during, and after the intervention (Table 3).

This study is ancillary to an existing IRB-approved prospective longitudinal observational study which enables and accelerates the process of developing, translating and disseminating innovative Care Partner interventions facilitated by technology. The ORCASTRAIT study (IRB#20236) is currently enrolling 120 dyads (patients with dementia, and a family Care Partners). ORCASTRAIT uses sensors and other technologies in participants' home setting to monitor and detect (through novel algorithms) early changes in health, cognitive function, activity, and behavioral-functional signatures of patients and Care Partners. The proposed ancillary study will target informal Care Partners enrolled in ORCASTRAIT, and follow changes in their stress and health over the study period. This ancillary study will incorporate data from the parent study, will add the Care Partner (STELLA) intervention and measure Care Partner coping with an additional 5 surveys to the electronic (online) surveys that informal Care Partners are already completing over the parent study period.

4. Study Population

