Care Partners and their family members with dementia will participate in STELLA for a total of 18 months (Table 3); however, most of the participatory effort will occur in the first two months. In this two-month period, Care Partners will participate in the STELLA intervention and complete surveys listed in Table 4. In the next 16 months, we will ask them to complete on-line surveys per the schedule noted in Table 4. Care Partners will receive an email from the study team asking them to open the Qualtrics or REDCap survey. Once they are in Qualtrics or REDCap, they will receive a welcome message from the PI and study team (see invites and reminder messages). Their family members with dementia will not have any STELLA activities, but we will be analyzing their data during the 18-month period.

All STELLA sessions will occur via videoconferencing and will be video-recorded. The video-

conferencing and recording will occur via the OHSU Telehealth Department's HIPAA-compliant, secure systems. Participants will use their own computers to access the study. However, some Care Partners may need to borrow a device. If this is the case, we will lend them a Chromebook. Chromebooks require an internet connection to function and a Google email (Gmail) account to use the STELLA application. We will advise participants in the consent form that they may use their own Gmail account but there is a risk that some of their personal information may be stored on the Chromebook. Alternatively, we can create a Gmail account for them.

Table 2: STELLA Curriculum

Week	Format	Topic
1	One Guide to one Care Partner	Introduction to dementia and behavior management
2		Addressing behaviors
3		Care Partner care
4		ABCs in action
5*	One Guide with up to 4 Care Partners	Communication and dementia
6		Pleasant events
7		Putting it altogether
8		Moving forward, staying connected

*There may be a 2 week break between weeks 4 and 5 if there are scheduling challenges

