Intervention (4 weekly sessions)	Meet with for 4 weekly sessions, beginning with Session 1 . (see Table 2)	After Mercury Baseline survey completed
Starlet Survey (Survey 2)	Electronic assessment of depression, burden	1 month after Session 1
Intervention (4 weekly sessions)	Meet with Guide and up to 4 other Care Partners for 4 more weekly sessions (See Table 2)	After session #8
Venus Survey (Survey 3)	Full assessment, including program survey	2 months after Session 1
Post-STELLA Assessment	Complete personalized target problem assessment via Qualtrics or via video or phone call with a Research Assistant	After Venus survey completed
Focus Groups	Optional focus group to provide study team with feedback	After Venus survey completed
Earth Survey (Survey 4)	Full assessment (Table 4)	6 months post-intervention
Earth Survey (Survey 5)	Full assessment (Table 4)	12 months post intervention
ORCASTAIT Surveys	Cost, burden as described in ORCASTRAIT Protocol	Weekly, while in ORCASTRAIT

Phase 1

Measures. Aim 1: Feasibility will be assessed by measuring how many Care Partners who start the program successfully complete it. Care Partners will fill out our telehealth survey that asks them about acceptability.^(23, 24) Acceptability will also be assessed qualitatively using focus groups.⁽²⁵⁾ The focus groups will be conducted via videoconferencing and will be recorded and transcribed for analysis.^(15, 16)

Aim 2: Standard quantitative measures that were used in the earlier pilots^(15, 16) will be used to provide preliminary evidence for efficacy. The quantitative measures are grouped into 5 surveys: Mercury Baseline, Starlet, Venus, Earth (6 months post intervention) and Earth (12 months post intervention). Along with the ORCASTRAIT Living Lab suite of measures (demographics, activity, time with person with dementia, sleep-related behaviors), we assess burden using the RMBPC⁽²⁶⁾ and the 22-item Zarit Burden Interview (ZBI). To provide focus for the intervention, each Care Partner will identify and rate 2-3 specific target problems to address in STELLA. Pre-death grief will be assessed with the Marwit Meuser Caregiver Grief Index, Short Form (MMCGI-SF).⁽²⁷⁾ Care Partner plans for person with dementia placement will be assessed with the

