revised Desire to Institutionalize (DTI) scale.⁽²⁸⁾ Care Partner depression will be measured with the CESD-10⁽³⁰⁾ and role captivity will also be assessed.⁽³¹⁾ In addition to subjective assessments, we will evaluate the effect of STELLA on digital behavioral biomarkers (activity, time spent together and sleep) obtained from the ORCASTRAIT platform. Total daily activity, time together and alone, and sleep duration, will be assessed prior to, during, and after the intervention. Care Partners will complete all assessments electronically. A secure link to each assessment will be emailed to each CP. We will ask the CPs to complete the assessments within 5 days of receiving the email. If they do not, we will call them to assess their situation. If they do not complete surveys as outlined on the times listed in Table 3 they may not continue with the intervention.

Aim 3. To identify which components of STELLA are most helpful to Care Partners, we will assess the mechanisms of action for reducing burden, depression and grief and improving cognitive function and sleep. Care Partners will complete the surveys (**Table 3**) before the intervention, after Session 4 and after the intervention. An analysis of objective data (**Figure 1**) will also be done during the intervention. We will ask Care Partners in our focus groups to report what they found most helpful about STELLA.

Table 4: Subjective Assessment Descriptions

Measure	Description
Mercury Baseline	
Demographics	Demographics, including hours/week caregiving
Revised Memory & Behavioral Problems Checklist (RMBPC) ²³	Measure of frequency and reactivity to behavioral and psychological symptoms of dementia ²³
Personalized target problem assessment	Care partner-identified targeted problem assessment
Zarit Burden Interview (ZBI) ³³	4-item measure of burden
Center for Epidemiologic Studies Depression Scale (CESD-10) ³⁴	10-item depression measure
Marwit Meuser Caregiver Grief Index-Short Form (MMCGI-SF) ³⁵	Care partner pre-death grief ³⁵
Placement plan scale ³⁷	One-item assessment of plans for placement for family member with dementia ³⁷
QoL AD ³⁶	13-item assessment of quality of life for both the care partner and the person with dementia.
Starlet Survey	
ZBI ³³	
CESD-10 ³⁴	
Venus Survey	
RMBPC ²³	
 • See Baseline for descriptions • Baseline: 
 + STELLA contact survey + Experience Survey -Demographic survey
Personalized target problem assessment	

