Aim 2: Efficacy will be assessed by calculating changes in the subjective scores before, during and after the intervention using linear regression models and controlling for age, sex and education. Since this is an exploratory (proof-of-concept) study with a small sample size, we do not expect statistically significant findings, but pre-post change and standard deviation of the change will be used to calculate the sample sizes for the next stage, a RCT (NIH Stage II⁽³²⁾, Phase 1) study.

Objective digital behavioral biomarker data collected from the ORCASTRAIT Living Lab (e.g., daily activity (steps), total sleep time, times together) will be assessed before, during and after the intervention and compared to subjective findings. Simple Spearman correlations will be used to explore the relationship of the objective continuous sensor-derived data to the subjective data, where the continuous objective digital data is collapsed to mean values which will serve as a point estimate prior to, during and after the intervention. We will compare the shift in the distribution of each of the digital behavioral biomarkers from baseline to identify relative changes during and after the intervention. We will compare the objective and subjective findings of the dyad to identify trends that correlate with burden (**Figure 1**)⁽³³⁾.

Aim 2 Anticipated Results and Implications. We anticipate that STELLA will reduce Care Partner burden and grief and improve family quality of life. These improvements in turn will decrease

Care Partner desire to place family members in long-term care. We expect these findings will be supported by both subjective and objective data.

Aim 3: Before Session 5, subjective and objective data (**Table 4**) will be compared to pre, mid- and post-intervention data to identify trends. Qualitative data will be gathered during the focus groups. Participants will be asked what they thought was most helpful about the intervention and what they thought of the format. The objective and subjective results will be used to identify which components of STELLA were most effective and which need to be modified to improve the potency of future iterations.

Aim 3 Anticipated Results and Implications. We expect to see an improvement in the objectives and subjective data, and we expect that we will need to revise the STELLA intervention. We will use information from the focus groups and the accrued data to revise as needed.

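### Table 3 dates the mid-point survey (Starlet) on or just after Session 5 when sessions run weekly without a gap, so scheduling alone decides whether it follows no group session or one

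*Combined protocol and SAP*

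**What the plan says.** Section 5 (Procedures Involved) describes eight weekly sessions: four one-to-one with a Guide, then four in a small group. Table 3 places Starlet, which carries the ZBI and the CESD-10, between the two blocks and makes it due "1 month after Session 1". Venus, the full post-intervention survey, is due two months after the same session. Neither date is said to move when sessions move.

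Sessions can move. The footnote to Table 2 reads "There may be a 2 week break between weeks 4 and 5 if there are scheduling challenges". The paragraph headed The STELLA Intervention allows a pause of at most two weeks before Session 5 and some rescheduling in general.

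Elsewhere the surveys are placed by event. Measures, Aim 3 puts them "before the intervention, after Session 4 and after the intervention". Analytic Plan, Phase 1, Aim 3 opens its comparison with "Before Session 5, subjective and objective data".

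Measures, Aim 2 asks Care Partners to "complete the assessments within 5 days of receiving the email" and adds "If they do not, we will call them to assess their situation". Its closing sentence says that those who miss the survey times in Table 3 may not go on with the intervention, so the Table 3 dates are the operative ones.

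A month is not defined. Section 3 says "Care Partners will participate in an 8-week intervention" and Section 5 says "In this two-month period, Care Partners will participate in the STELLA intervention", which suggests four weeks, but a calendar month is equally open.

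**The concern.** The row order of Table 3 and the Aim 3 analysis wording both suggest a reading taken after the one-to-one block and before the group block. The Table 3 date does not deliver that on the default schedule, and it delivers something different when the gap is used.

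Starlet is the only STELLA survey at the change of format, and Aim 3 uses the survey and sensor results to judge which parts of the programme worked best. If some Care Partners answer after four sessions and others after five, the mid-point no longer marks the end of one-to-one work. The Background (Phase 1) gives this some weight: the pilots reduced burden but not depression, the protocol links that to support ending after Session 8, and the group format was added in response. Depression at the point where groups begin is therefore a reading the study has reason to want clean.

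**Working it through.** The plan states no figure that bears on this, so there is nothing to reproduce. The check is calendar arithmetic.

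**Inputs**
- Session 1 = day 0 and sessions are weekly (Section 5), so Session 4 = 3 × 7 = day 21.
- With no gap, Session 5 = day 28 and Session 8 = day 49.
- One month = 28 days (four-week reading) or 28-31 days (calendar). Two months = 56 or 59-62 days.
- Gap at its longest: either a 14-day interval in total between Sessions 4 and 5 (Session 5 on day 35), or 14 days added to the weekly interval (Session 5 on day 42). The wordings in Table 2 and Section 5 do not settle which.
- Completion request: 5 days from the email (Measures, Aim 2).

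**Due date minus session date, in days**

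| Schedule | Session 5 | Starlet, 4-week | Starlet, calendar | Session 8 | Venus, 4-week | Venus, calendar |
|---|---|---|---|---|---|---|
| No gap | 28 | 28 − 28 = 0 | 0 to +3 | 49 | 56 − 49 = +7 | +10 to +13 |
| 14-day interval in total | 35 | 28 − 35 = −7 | −7 to −4 | 56 | 0 | +3 to +6 |
| 14 days added | 42 | 28 − 42 = −14 | −14 to −11 | 63 | −7 | −4 to −1 |

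**Starlet.** With no gap, it is never due before the day of Session 5. Taking every start date from 2021 to 2024 as equally likely (an illustration), a calendar month puts it strictly after that day for (841 + 500 + 33)/1,461 = 94% of dates. With the gap at its longest, it is due 4-14 days before Session 5.

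**Starlet answers.** With no gap, the 5-day request ends on day 28 + 5 = 33 to day 31 + 5 = 36. An answer on day 28 follows 0 or 1 group session; on days 29-34 it follows 1. Two are possible only on days 35-36, because Session 6 is on day 35.

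**Against the event wording.** Day 28-31 is 7-10 days after Session 4, so the Measures wording is met by default. It would fail only if rescheduling moved Session 4 by more than 7 days (four-week month) or more than 7-10 days (calendar month).

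**Venus.** If the gap adds g days, Session 8 is on day 49 + g. Venus is due before it when 49 + g > 56, that is g > 7 (four-week month), or when 49 + g > 59 to 62, that is g > 10 to 13 (calendar month). If the gap is a 14-day interval in total, Venus falls on or after Session 8 unless other sessions are rescheduled.

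**The case against.** The case against is substantial.

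- **Design.** The study is exploratory with no randomised comparison group, the order of components is fixed, and the Analytic Plan does not expect significant results. Component findings stay descriptive whatever the survey date. This stands, and it limits the weight of the point.
- **Other data.** Table 3 also lists weekly ORCASTRAIT surveys that cover burden, and sensors and focus groups inform Aim 3. This stands too, although the weekly burden instrument is not shown. Depression is what depends most on Starlet.
- **Wording.** The sentence in the Aim 3 analysis is too loosely built to fix a date, and the date in Table 3 does meet the Measures wording. Both are true. The conflict with Table 3's own row order remains.
- **Late answers.** The sentence on not continuing ties sessions to survey completion, so late answers are not simply left to vary. That is fair. But with no gap, an on-time answer can already follow Session 5.
- **Fixed dates.** A constant distance from Session 1 is a legitimate choice. It is, but the group sessions attended must then be recorded for the reading to be interpretable.

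A reader might infer that Venus is affected just as Starlet is, or that the post reading is routinely taken before the programme ends. The documents do not support that. With no gap, Venus falls 7-13 days after Session 8. It precedes Session 8 only if the gap is read as added days and is long enough, or if sessions slip. A reader might also infer that the SD used to size the later RCT is distorted by a known amount. No such amount can be derived.

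**Conclusion.** The point holds for Starlet and is secondary for Venus. On the default schedule, Table 3 dates the mid-point survey 0-3 days after Session 5 (0 on a four-week month). With the longest gap, the same rule dates it 4-14 days before Session 5. By due date the reading therefore follows 0 or 1 group session, and scheduling alone decides which.

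This rests on sessions otherwise running weekly and on the two readings each of month and gap set out above. The documents do not say how often gaps or rescheduling occur, so the share of Care Partners in each state is unknown. It should be corrected, because the Table 3 times govern conduct and the remedy is small. It does not make Aim 3 unanswerable.

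**What to change.** 1. **Starlet.** In Table 3, tie it to Session 4: send it after that session and ask for completion before Session 5. Keep late answers, record how many group sessions preceded each answer, and show the mid-point comparison with and without the late ones. With no gap, sending on day 21 ends the 5-day request on day 26 and leaves day 27 for the follow-up call.
2. **Venus.** Do not send it until Session 8 has taken place, or send it at the two-month date if the Care Partner has stopped sessions. Record days since Session 8 and report them with the pre-to-post change. State whether a month is four weeks or a calendar month, since this date still depends on it.
3. **Reconcile.** The Table 3 row for the second block of sessions, which is itself due only once Session 8 is over; the two gap wordings (Table 2 footnote and The STELLA Intervention); the timing in Measures, Aim 3 and in Analytic Plan, Aim 3; and the sentence on continuing the intervention when Table 3 times are missed, which bears on how late answers are handled.

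**Cost.** One changed trigger, one added condition and a few recorded variables. On the default schedule Starlet can come up to 7-10 days earlier (day 21 instead of 28-31), which leaves less time to try out Session 4's work, and its distance from Session 1 will vary with rescheduling. Venus is delayed when a long gap or rescheduling pushes Session 8 past the two-month date. Much of the variation in days since Session 8 will remain, which is why it should be reported.

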Assessing Acceptability, Cost, and Efficacy of STELLA-Support via Technology: Living and Learning with Advancing AD

01/31/2022

NCT04335110

Protocol Title:

Assessing Acceptability, Cost, and Efficacy of STELLA-Support via Technology: Living and Learning with Advancing AD

Objectives

STELLA (Support via TTechnology: Living and Learning with Advancing Alzheimer's disease and related dementias) is a multicomponent video-conference based intervention designed to facilitate effective management of behavioral and psychological symptoms of dementia (BPSD). In the STELLA intervention, professionals ("Guides") meet with family members ("Care Partners") caring for persons with dementia. Working together, the Care Partners and Guides identify strategies to address upsetting behaviors in the moderate to late stages of dementia. The goal of this intervention is to reduce upsetting behaviors and thus care partner burden including costs.

The specific aims of this study are:

Phase 1

1. Using quantitative and qualitative approaches, assess feasibility and participant acceptability of (a) STELLA, and (b) the assessment methods (subjective measures and unobtrusive objective monitoring).
2. Using quantitative strategies, assess the preliminary effect of STELLA on (a) the affective impact of caregiving, Care Partner cognitive function and person with dementia quality of life, and on (b) Care Partner and person with dementia objective digital behavioral biomarkers (activity, sleep and time together).
3. Test the feasibility of employing digital behavioral biomarker data, combined with qualitative Care Partner feedback, to assess mechanisms of behavior change before, during and after the STELLA intervention.

Phase 2

1. Quantify the costs of delivering the STELLA intervention.
2. Quantify the cost efficacy of STELLA in relation to BPSD frequency and CP reactivity and assess the relationship between costs, BPSD, and care partner burden.

H1: There is a relationship between BPSD and cost: More BPSD behaviors and more CP reactivity to the BPSD are associated with higher out-of-pocket and implicit costs for families living with dementia.

H2: There is a relationship between out-of-pocket and implicit costs and objective measures of burden identified in the ORCASTRAIT Living Lab continuous home assessment. Higher objective burden will correlate with higher implicit and out-of-pocket costs.

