a. Care Partners and Persons with Dementia. Up to 40 Care Partners and their 40 care-recipients with ADRD will participate in this study. The primary focus of this study is on Care Partners, however, we will gather subjective and objective data on participants with ADRD to assess the effect of the intervention on Care Partner affective responses to caregiving and quality of life for both. STELLA participants will be recruited from the existing cohort of patients, and their Care Partners, who are enrolled in the ORCASTRAIT Life Laboratory (OSLL).

There has been no pilot testing of STELLA with non-English speaking care partners, and all materials have been tested in English. Therefore, only English-speaking participants are included in STELLA.

b. Inclusion and exclusion criteria. The research team will assess eligibility of interested parties based on the criteria listed in Table 1. In the event of a screen failure, data collected during screening will be destroyed at the end of the study. The recruitment team will track the number of care partners contacted for the study, the number consented, the number of those that dropped out and the number of those that completed the entire intervention.

Table 1: Inclusion/Exclusion Criteria

Participant	Inclusion	Exclusion
Care Recipient	
 Diagnosis of ADRD, moderate to late stages Exhibits 2 or more behaviors listed on RMBPC¹⁶ that are bothersome to the Care Partner and occur 3 or more times/week at study enrollment Family member of Care Partner (this can be a relative, spouse or close kin that is considered family) 	
 Dementia not related to ADRD Unable to leave Care Partner during Partner training Early stage dementia, as defined by MoCA of about 15/30 or higher.

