Surveys and subjective assessments will be administered in person via video conferencing or delivered to Care Partners email via a secure system.

Care Partners will be assigned a study ID number which will be used to identify all documents. The key to study ID numbers will be kept in a secure file on a secure OHSU computer.

After the intervention and the second assessment, Care Partners will be asked to participate in a focus group. No less than 3 and no more than 10 Care Partners will participate in each focus group. Focus group participation will be assigned sequentially (e.g., Care Partners 1 through 6 will be in the first focus group) unless Care Partner availability prevents otherwise. The focus groups will be moderated by the PI or a designated team member.

Care Partners who are unable to complete all 8 training sessions will remain in the study and we may collect the data noted in Table 4. These Care Partners may join a focus group if they choose. Care Partners who do not complete any trainings, or are unwilling or unable to adequately follow study instructions and participate in study procedures, will be withdrawn from the study. We will retain and analyze any data from their participation. They may also be asked to complete the assessments, despite not completing all of the trainings.

For some participants, internet connectivity may be problematic. Every effort will be made to help Care Partner maintain a good connection for each visit. A research team member will test their ability to connect and the quality of their connection prior to Session 1 and later visits if needed. In some cases,

at PI discretion, computer (e.g., Chromebook) may be loaned to the research participant for use in the study if available. If, after multiple efforts, a Care Partner cannot maintain a reliable connection for a telehealth visit, they will be excused from the study. They will be allowed to keep the STELLA Handbook.

Guides will be trained by the PI using the Guide Handbook. The PI or other study staff will review their videos for fidelity, using the Consultant Adherence Checklist. During STELLA, videos will be reviewed by the study team for fidelity and team discussion.

Table 3: STELLA Activities

Activity	Description	Due
Preliminary session	Set up and test videoconferencing link	After consent completed
Mercury Baseline (Survey 1)	Baseline assessment (Table 4)	Prior to intervention start

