ZBI ³³	
CESD-10 ³⁴	
MMCGI-SF ³⁵	
Placement plan scale ³⁷	
QoL-AD	
STELLA contact	STELLA care partner contact post intervention
STELLA Experience Survey	16-item + comments on satisfaction, privacy, ease of use
Earth Assessment	
RMBPC ²³	
 • See Baseline for descriptions • Baseline: 
 + STELLA contact survey -Experience Survey
ZBI ³³	
CESD-10 ³⁴	
MMCGI-SF ³⁵	
Placement plan scale ³⁷	

QoL-AD	-Demographic survey
STELLA contact	

Phase 2

Aim 1. Quantify the costs of delivering the STELLA intervention. This will measure the direct costs of delivering the intervention (wage multiplied by time of all personnel supporting the intervention) as well costs of technology and equipment, and any in-kind donations of equipment or time to support the intervention.

Aim 2. Quantify the cost efficacy of STELLA in relation to BPSD frequency and CP reactivity and assess the relationship between costs, BPSD, and care partner burden.

Out-of-pocket costs for participating dyads will be collected using an addition to the weekly online ORCASTRAIT survey. CPs will be queried about personal funds spent on health care services, co-pays, medications, or equipment. CP time dedicated to these care-related activities will also be collected. Implicit costs for families will be calculated by multiplying the average weekly hours of care provided by the CP by the average hourly wage of paid caregivers in Portland, Oregon (approx. \$29).

Analytic Plan.

Phase 1

Aim 1: Feasibility will be assessed by calculating the proportion of enrolled Care Partners who completed the full intervention. Reasons for drop-out and discontinuation will be investigated carefully. Focus group transcriptions will be analyzed for themes of acceptability using narrative analysis.⁽²⁵⁾

Aim 1 Anticipated Results and Implication. We anticipate that the Care Partner will find the STELLA intervention feasible and acceptable. This will provide foundational information for future proposals.

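### Acceptability data from Care Partners who leave early are optional or undescribed, so the Phase 1 Aim 1 result may over-represent completers

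*Combined protocol and SAP*

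**What the plan says.** The Objectives set Phase 1 aim 1 as to "assess feasibility and participant acceptability of (a) STELLA, and (b) the assessment methods". Section 5 (Measures, Aim 1) names two sources for acceptability. The first is a survey: "Care Partners will fill out our telehealth survey that asks them about acceptability". The second is focus groups.

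**Survey.** Table 4 lists the STELLA Experience Survey ("16-item + comments on satisfaction, privacy, ease of use") under Venus. The Starlet survey at one month holds only the ZBI and the CESD-10, and the Earth surveys at 6 and 12 months after the intervention drop the "Experience Survey". Table 3 dates Venus two months after Session 1. I take the telehealth survey in Measures, the program survey in Table 3 and the Experience Survey in Table 4 to be one instrument.

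**Focus groups.** Table 3 describes an "Optional focus group to provide study team with feedback", due once Venus is complete.

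**Early leavers.** The Section 5 text before Table 3 distinguishes three groups:

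- Those who cannot finish all eight sessions stay in the study. Table 4 data *may* be collected from them, and they *may* join a focus group.
- Those who complete no training, or are "unwilling or unable to adequately follow study instructions and participate in study procedures, will be withdrawn from the study". Their existing data are kept and analysed, and they *may* be asked for assessments.
- Those who cannot hold a reliable connection after repeated attempts are excused from the study. No later assessment is described for them.

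**Analysis.** The Analytic Plan for Aim 1 computes feasibility over enrolled Care Partners, undertakes to look into reasons for drop-out, and analyses the focus-group transcripts by narrative analysis. It gives no analysis, denominator or missing-data rule for the Experience Survey.

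**The concern.** Whether someone is still in the study and answering at two months can depend on what the survey measures. The instrument covers satisfaction, privacy and ease of use. A Care Partner who found the programme unhelpful has a reason to stop. One who declines the questionnaires is giving evidence on acceptability of the assessment methods, the second half of the aim. One whose connection keeps failing has had a poor experience of ease of use in a video-delivered programme, whatever they thought of its content.

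If such people are mostly absent from both sources, the result describes those who stayed and replied, whereas the objective refers to participants. The plausible direction of error agrees with the plan's own expectation that STELLA will be found feasible and acceptable, which it intends to use as a foundation for future proposals.

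**Working it through.** The plan states no acceptability target, expected drop-out rate or sample-size calculation, so there is no figure to reproduce. The check has two parts.

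**1. Routes into the acceptability data**

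| Care Partner | Experience Survey | Focus group |
|---|---|---|
| Completes all sessions | Scheduled at Venus | Optional, after Venus |
| Misses some sessions, stays in study | *May* be collected; Venus is dated from Session 1, so it can still reach them | *May* join |
| Withdrawn | *May* be asked | Not described |
| Excused for connection failure | Not described | Not described |

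Only the first row has scheduled survey collection without a qualifier. No exit version of the survey appears anywhere.

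**2. Illustration of size**

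From the documents: N = 40, the maximum (Section 4a: "Up to 40 Care Partners and their 40 care-recipients with ADRD will participate in this study"), treated here as all starting.

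Assumed, because the documents give no values: acceptability in completers pc = 90%; acceptability in leavers pn = 30% or 60%; leavers d = 4, 8 or 12 (10%, 20%, 30%). Summarising the survey as a percentage who find STELLA acceptable is also an assumption, since the plan defines no such statistic.

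- All starters: T = [(N − d)·pc + d·pn] / N
- Observed if no leaver answers: pc = 90%
- Observed if half the leavers answer: H = [(N − d)·pc + (d/2)·pn] / (N − d/2)
- Overstatement: observed minus T

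| d | pn | T | Overstatement, none answer | H | Overstatement, half answer |
|---|---|---|---|---|---|
| 4 | 30% | (32.4 + 1.2)/40 = 84.0% | 6.0 | 33.0/38 = 86.8% | 2.8 |
| 4 | 60% | (32.4 + 2.4)/40 = 87.0% | 3.0 | 33.6/38 = 88.4% | 1.4 |
| 8 | 30% | (28.8 + 2.4)/40 = 78.0% | 12.0 | 30.0/36 = 83.3% | 5.3 |
| 8 | 60% | (28.8 + 4.8)/40 = 84.0% | 6.0 | 31.2/36 = 86.7% | 2.7 |
| 12 | 30% | (25.2 + 3.6)/40 = 72.0% | 18.0 | 27.0/34 = 79.4% | 7.4 |
| 12 | 60% | (25.2 + 7.2)/40 = 81.0% | 9.0 | 28.8/34 = 84.7% | 3.7 |

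Overstatements are in percentage points. If pn = pc, T and H both equal 90% and the overstatement is zero.

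Bounds that assume nothing about leavers' views: with 8 silent leavers and 90% among the other 32, acceptability over all 40 lies between 28.8/40 = 72% and (28.8 + 8)/40 = 92%.

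**The case against.** A reader might infer from Tables 3 and 4 alone that anyone who stops early is excluded from the acceptability result by design, and that the result is therefore biased upward. The documents do not support that.

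- Section 5 keeps partial completers in the study and opens both the survey and the focus groups to them. It also permits assessments after withdrawal. These routes collect new data and go beyond keeping what was already gathered.
- Venus follows the calendar from Session 1 and does not depend on reaching Session 8.
- The rule on late surveys (Measures, Aim 2) can stop the intervention. It does not say that the person leaves the study or misses Venus. Late responders are also telephoned.
- Connection failure need not mean dislike, and Section 5 offers telephone sessions as a fallback, which may reduce such exits.
- Attrition will be visible. Section 4b tracks numbers contacted, consented, dropped out and completed, and feasibility is reported over enrolled Care Partners.
- Every input to the illustration except N is assumed, and this is a small proof-of-concept study.

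These points stand, and they rule out a claim of systematic exclusion or of a demonstrated bias. They do not close the gap. Permission to collect is not a plan to collect, and excused Care Partners lack even the permission. The telephone call and the review of drop-out reasons have no stated acceptability content. A completion rate shows how many left, not how they rated the programme.

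**Conclusion.** The point holds in a limited form. Acceptability is surveyed once, at two months, and Table 3 puts the optional focus groups later still. Collection from partial completers and withdrawn Care Partners is at the team's discretion, and none is described for those excused. With no denominator or missing-data rule for the Experience Survey, the result may over-represent completers and may be tilted upward.

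Neither direction nor size is established by the documents. The direction rests on leavers being less satisfied than completers. Under the assumptions shown, the overstatement runs from 3 to 18 points if no leaver answers and from about 1 to 7 points if half do, and it vanishes if leavers rate STELLA as completers do. The point concerns only the acceptability data, not the pre-post outcome scores.

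**What to change.** **Collection (Section 5 text, Tables 3 and 4).** Replace the discretionary wording with a commitment to send the existing 16-item Experience Survey to every Care Partner who starts the programme, including those withdrawn or excused, at the earlier of Venus or the date they leave. Offer early leavers a focus-group place.

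**Analysis (Analytic Plan, Phase 1 Aim 1).** Report the Experience Survey with the number of responders over all Care Partners who started, split into completed and left early. Where leavers do not answer, describe the result as applying to responders. Best- and worst-case bounds are optional. Define who counts as having started, because Measures refers to those who start and the Analytic Plan to those enrolled.

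**Reconcile.** The Section 5 text places focus groups after the intervention and the second assessment, while Survey 2 in Table 3 is Starlet and Table 3 places the groups after Venus.

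**Cost.** One extra electronic send of an existing survey to those who leave early, and a few lines of analysis text. Some leavers will not answer, and the acceptability result may be less favourable.
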